8.7.1. Additional Exploratory Analyses of ALT

8.7.1.1. Change from Baseline in ALT

Analyses will also be carried out using a REML based MMRM to evaluate the effect over time on treatment using the Efficacy Analysis Set. The dependent variable will be the percent change

A large black rectangular redaction box covers the majority of the page content, starting below the header and ending above the footer. It is positioned in the center of the page and spans most of its width.

8.7.1.3. ALT Responder Analyses

The number and percentage of patients meeting the following definitions of responder and non-responder based on ALT will be summarized by treatment group at Week 12 [REDACTED]

- Change from baseline
 - Responder: Decrease in ALT of at least 17 U/L
 - Non-responder: all other non-missing values
- Percent change from baseline
 - Responder: Decrease in ALT of at least 30%
 - Non-responder: all other non-missing values
- ALT result
 - Responder: Values 0 to ≤ 30 U/L
 - Non-responder: Values > 30 U/L

In addition, for each definition of response, the number and percentage of patients who ever met the criteria over the course of the study will be summarized.

A Chi-square test at each post-baseline visit will be used to compare pooled TERN-101 (All TERN-101) and placebo, and each pairwise comparison between placebo and each active dose of TERN-101. [REDACTED]

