Of the 96 patients randomized, 24 patients will take part in an intensive PK and pharmacodynamic (PD) collection after the first dose and after the last dose of study drug. This includes 6 patients at each TERN-101 dose level, and 6 patients in the placebo group. Patients who are not participating in the PK/PD sub-study will have trough PK/PD sampling only.

The total duration of study participation will be approximately 24 weeks, consisting of an 8-week Screening Period, a 12-week Treatment Period and a 4-week Follow-up Period.

Disclosure Statement:

This is a parallel-group treatment study.

Number of Patients:

Approximately 96 patients will be randomly assigned to treatment with TERN-101 tablet or matching placebo.

Patients who are randomized but do not receive study drug for any reason may be replaced.

Study Centers Planned:

Approximately 40 centers in the United States.

Intervention Groups and Duration:

The total study duration will be approximately 24 weeks, consisting of an 8-week Screening Period, a 12-week Treatment Period and a 4-week Follow-up Period.

Screening Period

The 8-week Screening Period initiates upon signing an Informed Consent, at which point eligibility criteria will be reviewed. Each eligible patient will be scheduled for Week 0/Day 1.

Treatment Period

The 12-week double-blind, randomized Treatment Period will initiate at Week 0/Day 1 after confirming eligibility. The blinded study drug (TERN-101 tablet or placebo) will be orally administered once daily in the morning, without regard to food.

Patients will return to the site at Weeks 2, 4, 6, 8, and 12 for safety and laboratory assessments. Study drug will be dispensed at Week 0/Day 1, Week 4, and Week 8. Week 12 is the last day of treatment.

Intensive PK/PD sampling will be performed in 24 patients participating in the PK/PD sub-study after the first dose (Week 0/Day 1) and after the last dose of study drug (Week 12).

[figure not shown]
Imaging (MRI-PDFF) will be completed at Week 0, Week 6, and Week 12. An MRI is performed at early termination (ET) only if not done within the prior 4 weeks, and the patient has had at least 4 weeks of dosing.

Follow-up Period

All patients will return to site for follow up safety assessments at Week 16.

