5.1. Inclusion Criteria

Patients are eligible to be included in the study only if all of the following criteria apply:

1. Must be 18 to 75 years of age inclusive, at the time of signing the informed consent

3. Overweight or obese with a body mass index (BMI) ≥ 25 kg/m²

4. NASH by clinical diagnosis or biopsy as follows:

- a. For clinical diagnosis:

- i. Step 1: Liver stiffness measured by transient elastography of 7.6 - 21 kPa and controlled attenuation parameter (CAP) > 300 dB/m within 3 months prior to Screening (if results available within this timeframe, assessment does not need to be repeated at Screening).

- ii. Step 2: Patients meeting these and all other eligibility criteria will undergo MRI-PDFP and must have liver fat content $\geq 10\%$ for randomization.

- b. For biopsy diagnosis:

- i. Step 1: Fibrotic NASH (NASH CRN F1, F2, or F3) without cirrhosis diagnosed by biopsy within 2 years prior to randomization, with no subsequent treatment for NASH and stable weight ($< 5\%$ weight loss) since the time of the biopsy. Results from a previous study biopsy are permissible if drug was deemed non-therapeutic or patient received placebo.

- ii. Step 2: Patients meeting these and all other eligibility criteria will undergo MRI-PDFP and must have liver fat content $\geq 10\%$ for randomization.

5. All patients must have:

- ALT ≥ 43 IU/L for men and ≥ 28 IU/L for women
- MRI PDFP liver fat content $\geq 10\%$

6. Capable of giving signed informed consent as described in [Section 10.1.2](#), which includes compliance with the requirements and restrictions listed in the informed consent form (ICF) and in this protocol

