4.7.2. Definition of Baselines

The baseline value for statistical analyses of quantitative laboratory parameters is defined as the mean of all available evaluations, including any unscheduled or repeat assessments, prior to the first administration of study drug, unless otherwise specified. If there is only one evaluation prior to the first administration of study drug, then the available data from this evaluation will be used as the baseline value.

For glucose and lipid parameters, only assessments taken while fasting for 8 hours will be included in the baseline derivation.

The baseline value for analyses of qualitative parameters (e.g., normal/abnormal) is defined as the last evaluation prior to the first administration of study drug.

The baseline value for analyses of weight, body mass index (BMI), and electrocardiogram parameters is defined as the last evaluation prior to the first administration of study drug.

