5. ANALYSIS SETS

Table 6 defines the analysis sets to be used.

Table 6: Analysis Sets

| Analysis Sets | Description |
|----------------------|--|
| Screened | All patients who sign the informed consent form (ICF). |
| Randomized | All patients who are randomized into any one of treatment groups. Treatment assignment will be based on the randomized treatment. |
| [REDACTED] | [REDACTED] |
| Pharmacodynamic (PD) | All randomized patients who received at least 1 dose of study drug (TERN-101 or placebo) and for whom at least one post-baseline assessment of FGF19, 7αC4, [REDACTED] is available. Treatment assignment will be based on the treatment actually received. The PD analysis set will include patients with trough concentrations and with intensive PD sampling as part of the PK/PD substudy. |
| Safety | All patients who received at least 1 dose of study drug. Treatment assignment will be based on the treatment actually received. |
| Efficacy | All randomized patients who received at least 1 dose of study drug. Treatment assignment will be based on the randomized treatment. |
| Per Protocol (PP) | All randomized patients who have completed the study without any protocol deviations affecting the interpretation of the efficacy, PK, or PD results. Treatment assignment will be based on the treatment actually received. |

| Analysis Sets | Description |
|---------------------|--|
| Treatment Completer | 
All patients who complete 12 weeks of treatment with at least 80% compliance based on study drug accountability.
 
Treatment assignment will be based on the randomized treatment.
 |

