8.8.3.1. Fibrosis-4 (FIB-4) Score

The Fibrosis-4 (FIB-4) score helps to estimate the amount of scarring in the liver. The FIB-4 score is calculated as: $[\text{Age (years)} \times \text{AST (U/L)}] \div [\text{Platelet Count (10}^9/\text{L}) \times \text{ALT (U/L)}^{0.5}]$. Age at informed consent will be used. Lab values at each visit, from the same visit, will be used. The central lab calculation of FIB-4 will be used in analyses. Programming will also calculate the score programmatically for validation. Baseline AST, Platelets, and ALT will be the mean of all available evaluations, including any unscheduled or repeat assessments, prior to the first administration of study drug, per [Section 4.7.2](#). The FIB-4 score will be calculated at baseline and at Week 6, Week 12, and Week 16.

The FIB-4 score will be analyzed in the same manner as specified in [Section 8.8.3](#).

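### The exploratory ALT ≤30 U/L responder rule has no baseline condition in the visible text, so a patient already at or below 30 can count as a responder without any fall

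*SAP*

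**What the plan says.** SAP 8.7.1.3 sets out three ALT responder definitions.

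- Absolute change: "Responder: Decrease in ALT of at least 17 U/L".
- Percent change: a fall of 30% or more.
- ALT result: "Responder: Values 0 to ≤ 30 U/L", with every value above 30 U/L a non-responder.

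The first two are relative to baseline and the third is not. The section reports the rates at Week 12. It adds that, for each definition, "the number and percentage of patients who ever met the criteria over the course of the study will be summarized". It then compares pooled TERN-101 and each dose with placebo by Chi-square at each post-baseline visit.

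Three other provisions decide who can start at or below 30:

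- Protocol 5.1 requires "ALT ≥ 43 IU/L for men and ≥ 28 IU/L for women".
- SAP 4.7.2 defines a laboratory baseline as "the mean of all available evaluations, including any unscheduled or repeat assessments, prior to the first administration of study drug".
- SAP 5 defines the Efficacy set, which section 8.7 uses for ALT, as "All randomized patients who received at least 1 dose of study drug. Treatment assignment will be based on the randomized treatment". It sets no ALT condition.

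SAP 8.6 describes all testing as nominal and exploratory, without multiplicity adjustment. Parts of SAP 8.7.1 are redacted, including text in the opening sentence and at the end of 8.7.1.3.

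**The concern.** The word responder suggests that something improved. Under the third rule it need not have. The entry floor for women lies below the response threshold, so some women can meet the response criterion before the first dose and keep meeting it by staying where they are. Averaging the pre-dose values widens the window: a screening value of 28 and a Day 1 value of 26 give a baseline of 27.

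Men are in a different position. At an entry floor of 43 they have to fall to reach 30. The same label therefore asks for a real reduction in men and for none in the lowest-ALT women.

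At stake is how one exploratory rate can be read in each of its three uses (Week 12, each visit, ever met). The primary safety endpoints and the secondary ANCOVA of percent change in ALT do not use this rule.

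**Working it through.** The documents state no rate, effect size or power for this rule, so there is no planned figure to reproduce. IU/L and U/L are treated as the same unit.

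**1. From the documents alone**

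- Woman, 28 to 30: change +2 U/L, 2/28 = +7.1%. She is a responder under the ≤30 rule and fails the other two.
- Woman with baseline 30: the 30% rule needs 30 × 0.70 = 21 or less, and the 17 U/L rule needs 30 − 17 = 13 or less. The ≤30 rule needs no change.
- Man with baseline 43: he must fall 13 U/L, 13/43 = 30.2%, to reach 30.

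**2. How many patients (assumed inputs)**

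The documents give neither an ALT distribution nor a sex mix. Assumptions: log-normal ALT; medians 40 or 50 IU/L in women and 60 in men; between-person log-SD 0.45; within-person log-SD 0.15 or 0.20; entry floors applied to the screening value; baseline = mean of screening and Day 1. Elastography, liver-fat, biopsy, ALT-stability and upper ALT limits are not modelled. Results for untreated patients at Week 12, with 60% women and 24 per arm:

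| Women's median, within-person log-SD | Baseline ≤30, per arm | Rate as planned | Share of responders with baseline ≤30 | Share of responders with no fall |
|---|---|---|---|---|
| 40, 0.15 | 0.94 | 6.5% | 37% | 8.8% |
| 50, 0.15 | 0.51 | 3.7% | 33% | 8.1% |
| 40, 0.20 | 1.04 | 8.1% | 32% | 7.1% |
| 50, 0.20 | 0.54 | 4.8% | 26% | 5.9% |

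Responders with no fall, per arm = 24 × rate × share:

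- First row: 24 × 0.065 × 0.088 = 0.14.
- Last row: 24 × 0.048 × 0.059 = 0.07.

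Restricting to baseline above 30 takes the untreated rate from 3.7–8.1% to 2.5–5.8%. Among untreated responders with baseline ≤30, 90–97% fail both other rules.

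Varying the share of women from 50% to 70% gives 0.4 to 1.2 patients per arm with baseline ≤30. A women's median of 60 with log-SD 0.35, which is equally unsupported, gives about 0.14 per arm, with about 0.02 per arm showing no fall. The overall range is therefore roughly 0.1 to 1.2 per arm, or at most 1.2/24 = 5%. The affected patients are all women in these settings, so at 70% women the 0.14 with no fall becomes 0.14 × 70/60 = 0.16.

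**3. Bias**

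The expected difference between arms in patients already ≤30 is zero under randomisation. By chance, if 5% of patients are in this group, two arms of 24 differ by two or more such patients in about 30% of trials.

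**4. Power of this rule's own test**

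Two reasonable models give opposite directions.

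- Patients already ≤30 have the same chance (0.5 to 0.8) of a Week 12 value ≤30 in both arms. If they are a share f, the rate difference shrinks by (1 − f). With true rates of 10% v 40% and f = 5%, 30 points becomes 28.5. Power is 60–62% with all patients and 66% restricted.
- The drug lowers everyone's ALT by 20%, including theirs. In the four settings above, pairwise power is 0.249, 0.161, 0.220 and 0.163 as planned, against 0.232, 0.136, 0.208 and 0.144 restricted.

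**The case against.** The strongest reply is that the third rule is headed as an ALT result. It is by design a level-attained measure, placed beside two change-based rules and full descriptive summaries of change. That limits how far a reader could be misled, but the plan still calls the category responder and tests it as such.

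A second reply is redaction: a baseline restriction could be in the blacked-out text. This cannot be excluded. However, the bullets for this rule are fully visible and split all values at 30. The redaction in the opening sentence governs all three rules, so it is an unlikely place for a condition on one of them.

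A third reply is size, and it largely stands. The share of untreated responders who start at or below 30 (26–37% in the table) sounds large, but most of them did fall. Responders with no fall are well under one patient per arm. The size also depends on assumed distributions.

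A reader might also infer that the ever-met rate wrongly counts an off-drug visit. The Protocol synopsis says "Week 12 is the last day of treatment", and ALT is still measured later, since "The FIB-4 score will be calculated at baseline and at Week 6, Week 12, and Week 16". The documents do not support making this a defect. SAP 4.7.1 refers to sensitivity analyses of Week 16 assessments described in section 8.7.1, so that partly redacted section does address Week 16. The visible silence may be only redaction.

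**Conclusion.** The point holds as a minor classification fault. On the visible text, the ≤30 U/L rule labels a patient a responder whose ALT was already at or below 30 and did not fall, or rose. This carries into the Week 12 rate, the ever-met rate and the per-visit tests. That conclusion rests on the documents alone.

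Its size does not. Roughly 0.1 to 1.2 patients per arm of 24 with baseline ≤30, and about 0.02 to 0.14 per arm (at 60% women) who are responders with no fall, are illustrations under assumed ALT distributions and sex mix.

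Two stronger readings should be resisted. One is that the rule favours the drug: randomisation balances these patients in expectation, and only chance imbalance remains. The other is that the rule costs or gains power: the direction changes with what is assumed about drug effect in patients already ≤30, so power is no reason to decide either way.

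**What to change.** Add one sentence to SAP 8.7.1.3: response defined as ALT ≤30 U/L is reported among patients with baseline ALT above 30 U/L, for the Week 12 rate, the per-visit tests and the ever-met rate, with the number excluded given per arm. Excluded patients remain assessed under the other two rules.

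The cost is a subset flag and a denominator smaller by about 0 to 1 patient per arm, which then differs from that of the other two rules. There may be a very small change in power on this exploratory test, in either direction. SAP section 1 allows changes to planned analyses to be recorded in the study report without reissuing the plan. If the redacted text already restricts the rule, no change is needed.

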2.2.4. Treatment Assignment, Blinding, and Randomization Methodology

Patients will be randomized to TERN-101 or placebo using an Interactive Web Response System (IWRS). Approximately 96 patients will be randomized at an overall ratio of 1:1:1:1 into 4 groups receiving 5 mg (n = 24), 10 mg (n = 24), 15 mg (n = 24) TERN-101 tablet, or matching placebo (n = 24). Randomization will ensure 6 patients at each TERN-101 dose level and 6 patients in the placebo group are assigned to the PK/PD sub-study.

Investigators, patients, all study personnel, and the Sponsor will remain blinded to each patient's assigned dose group throughout the course of the study. The randomization codes will be provided to bioanalytics to allow for the exclusion of placebo patients from the PK assay.

Bioanalytics will not disclose the randomization code or the results of their measurements until the trial is officially unblinded.

Emergency unblinding procedures are outlined in Section 6.4.1 of the study protocol and in the unblinding plan.

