For log-normal data

[REDACTED] the geometric mean and geometric coefficient of variation (CV%) will also be presented. The precision of descriptive statistics will be as follows: mean, median, Q1, and Q3 to 1 more decimal place than the raw data, SD to 2 decimal places more than the raw data, the minimum and maximum to the same number of decimal places as the raw data, geometric mean to 3 significant figures, and geometric CV% to 1 decimal place.

[REDACTED]

Confidence intervals (CIs) will be provided and will be rounded to 1 decimal place, unless otherwise specified, in the table and listing shell. A full set of summary statistics will only be presented if there are 3 or more values available. If there are less than 3 values, only the min, max, and N will be presented. The other summary statistics will be denoted as not calculated (NC).

For tables where rounding is required, rounding will be done to the nearest round-off unit. For example, when rounding to the nearest integer, values \geq XX.5 will be rounded up to XX+1 (e.g., 97.5 will round up to 98), while values <XX.5 will be rounded down to XX (e.g., 97.4 will round down to 97).

All statistical tests comparing groups will be conducted at the 2-sided, 0.05 level of significance, unless otherwise specified. Summary statistics for each treatment group will be presented, as well as two-sided 90% and 95% CIs comparing groups will be provided.

Other general programming specifications are provided in [Appendix 1](#).

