8. EFFICACY ANALYSES

8.1. Adjustments for Covariates

For comparison of treatment groups with respect to change and percent change from baseline, analysis of covariance (ANCOVA)

will be used. The corresponding baseline value will be used as a covariate in the model.

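### The visible ALT responder tests take no account of baseline ALT; a baseline-adjusted difference in proportions for the 17 U/L and ≤30 U/L criteria would be a cheap efficiency gain, not the repair of an error

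*SAP*

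**What the plan says.** SAP Section 8.7.1.3 defines three ALT responder criteria:

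- on change from baseline: "Responder: Decrease in ALT of at least 17 U/L";
- on percent change: a fall of at least 30%;
- on the value itself: "Responder: Values 0 to ≤ 30 U/L".

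The comparison is given as follows: "A Chi-square test at each post-baseline visit will be used to compare pooled TERN-101 (All TERN-101) and placebo". Each dose is compared with placebo in the same way. The visible text names no covariate or stratum. The text directly after the chi-square sentence is redacted.

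For ANCOVA of change and percent change, SAP Section 8.1 says: "The corresponding baseline value will be used as a covariate in the model". Section 8.7 applies this to ALT at Week 12 and at each other post-baseline visit. As general conventions, Section 4.1 sets two-sided testing at 0.05 and adds: "as well as two-sided 90% and 95% CIs comparing groups will be provided". Section 8.6 treats all testing as nominal and exploratory, without multiplicity adjustment. On size, Section 2.2.4 says: "Approximately 96 patients will be randomized at an overall ratio of 1:1:1:1 into 4 groups", that is, 24 per arm. Protocol Section 9.2 sets this number without regard to power.

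**The concern.** Patients enter with ALT from 28 IU/L (women) or 43 IU/L (men) up to 5 x ULN (Protocol Sections 5.1 and 5.2). With a threshold on the absolute scale, where a patient starts affects whether the patient can respond at all. An unadjusted comparison leaves that variation in the error term. With 24 per arm, a chance difference in baseline ALT passes into the responder difference. The two absolute-scale criteria move in opposite directions: an arm that happens to start higher tends to show more 17 U/L responders and fewer ≤30 U/L responders.

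At stake is some precision in an exploratory comparison, and some protection against reading a chance baseline imbalance as a dose effect, or missing one. Nothing confirmatory depends on it.

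**Working it through.** **1. Dependence on baseline, from the definitions alone**

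- 17 U/L criterion: a baseline of 28 needs a fall of 17/28 = 61%; a baseline of 100 needs 17/100 = 17%.
- ≤30 U/L criterion: a woman entering at 28-30 already meets it with no change. A man at 43 needs (43 - 30)/43 = 30%; a baseline of 100 needs (100 - 30)/100 = 70%.
- 30% criterion: the required relative fall is the same at every baseline.

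**2. How much a chance imbalance moves the result**

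The SE of the difference in standardised baseline at 24 v 24 is sqrt(2/24) = 0.29 SD. In simulation, the 17 U/L responder rate rose by 0.14 to 0.21 per SD of log baseline. A 1-SE imbalance therefore moves the difference by 0.29 x 0.14 = 4 points to 0.29 x 0.21 = 6 points. For scale, with rates of 15% v 38% the crude difference has SE sqrt(0.15 x 0.85/24 + 0.38 x 0.62/24) = 12.3 points, which already includes this source of variation.

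**3. Power and type I error by simulation**

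The documents show no power, responder rate or SD for these tests, so there is no stated figure to reproduce.

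Inputs from the documents: the criteria, two-sided 0.05, 24 v 24 (pairwise) and 72 v 24 (pooled), and the ALT entry limits.

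Inputs assumed:
- log-normal baseline ALT with log-SD 0.30-0.60, capped at 200 U/L because no ULN is given; 60% women;
- placebo change -8%, active -25% or -35%; log-SD of change 0.25-0.35;
- with and without regression to the mean; no missing data.

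The chi-square test was compared with a linear model on the 0/1 indicator, with treatment and log baseline ALT as terms, at 2,000 trials per scenario.

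One scenario in full (72 v 24, median baseline 64 U/L, log-SD of change 0.35, active -35%, no regression to the mean):

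| Criterion | Placebo v active rate | Chi-square power | Adjusted power |
|---|---|---|---|
| 17 U/L | 25% v 60% | 86.4% | 88.2% |
| ≤30 U/L | 9% v 25% | 42.8% | 51.6% |
| 30% fall | 22% v 58% | 90.3% | 89.6% |

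Check of the first row by the normal formula: the pooled rate is (72 x 0.60 + 24 x 0.25)/96 = 0.5125. The null SE is sqrt(0.5125 x 0.4875 x (1/72 + 1/24)) = 0.118. The alternative SE is sqrt(0.60 x 0.40/72 + 0.25 x 0.75/24) = 0.106. Then (0.35 - 1.96 x 0.118)/0.106 = 1.12, or about 87%. This agrees with the simulated 86.4%, given rounded rates.

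Gain of the adjusted model over chi-square across the grid, in power points. Medians are given without, then with, regression to the mean:

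| Criterion | 24 v 24: range (medians) | 72 v 24: range (medians) |
|---|---|---|
| 17 U/L | +0.5 to +11.9 (1.9; 5.6) | +0.8 to +13.9 (2.1; 7.0) |
| ≤30 U/L | -1.5 to +9.7 (3.7; 2.5) | +0.5 to +15.4 (8.3; 6.0) |
| 30% fall | -2.2 to +0.6 (-1.4; 0.0) | -2.3 to +3.0 (-0.2; 0.3) |

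The correlation of response with log baseline was about +0.2 to +0.5 for 17 U/L and -0.3 to -0.6 for ≤30 U/L. Squared, that is 4-25% and 9-36% of the variance.

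Type I error with no treatment difference:

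| Criterion | Size | Chi-square | Adjusted linear model |
|---|---|---|---|
| 17 U/L | 24 v 24 | 4.4-6.8% | 4.2-6.1% |
| 17 U/L | 72 v 24 | 3.7-6.2% | 4.0-6.0% |
| ≤30 U/L | 24 v 24 | 0.9-5.3% | 1.4-4.7% |
| ≤30 U/L | 72 v 24 | 2.8-4.5% | 3.5-5.0% |

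Monte Carlo error is up to about 0.5 point for type I error and 1.1 points for power.

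**4. The choice of adjusted method matters**

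At 24 v 24, a logistic likelihood-ratio test had type I error of 6.3-7.5% for 17 U/L and 8.5-12.2% for ≤30 U/L. A logistic Wald test lost up to 30 points of power for ≤30 U/L, because responder counts are small. A Cochran-Mantel-Haenszel test split at 60 U/L held its error rate but gained less at 24 v 24 (-0.8 to +6.8 for 17 U/L, -2.0 to +5.6 for ≤30 U/L).

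**The case against.** The chi-square test is valid under randomisation. A reader might infer that leaving out the covariate makes it wrong or biased. The documents do not support that, because randomisation protects its type I error and chance imbalance is part of its stated uncertainty. The testing is exploratory, and no decision rule visibly rests on it. This stands in full.

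The same ALT data are already analysed on the continuous scale with baseline as covariate, including absolute change, which is the variable that the 17 U/L criterion dichotomises. SAP Section 7.2 also tabulates baseline ALT by arm, so an imbalance would be seen. This stands and lowers the importance of the point. Nor is adjustment uniform elsewhere: the Wilcoxon fallback in Section 8.7 is unadjusted, and the liver fat and cT1 responder analyses also use chi-square tests.

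A reader might infer that the plan has no adjusted responder analysis, or that it breaks its own promise of between-group intervals. Neither can be concluded. Text directly after the chi-square sentence is redacted, and the convention in Section 4.1 already covers intervals in general terms. All that can be said is that the visible part of Section 8.7.1.3 names no interval for the responder difference.

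A linear model for a binary outcome is an approximation. In one check, fitted values fell outside 0-1 in 70-100% of trials, and pooled 95% intervals for ≤30 U/L covered 97-98%. A separate run gave coverage of 94.5-97.6%. The intervals are thus at worst somewhat conservative, which does not defeat the proposal.

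**Conclusion.** The point holds as a modest efficiency improvement. In the visible text, the responder tests do not use baseline ALT, although the 17 U/L criterion depends on it moderately and the ≤30 U/L criterion moderately to strongly. Adjusting by the linear model typically gains about 2 to 8 power points, with a range from about -1.5 to +15, at a type I error close to that of the chi-square test. The 30% criterion has no case for change.

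These gains are not properties of the trial as documented. They rest on assumed responder rates, SDs, baseline distribution, regression to the mean and complete data, and a reader should not take any single figure as the gain to expect. The statement on type I error applies to the named linear model, not to adjustment in general. The dependence on baseline needs none of these assumptions for its direction, since it follows from the definitions and the entry limits.

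**What to change.** Unless the redacted text already does so, add to SAP Section 8.7.1.3, for the 17 U/L and ≤30 U/L criteria only, a linear model on the 0/1 responder indicator with treatment as a fixed effect and log baseline ALT as covariate. Report the adjusted difference in proportions with 90% and 95% CIs for each dose and for pooled TERN-101 versus placebo. Keep the crude counts and percentages and the chi-square test, so that the output stays comparable with the liver fat and cT1 responder tables. State that an unpenalised logistic likelihood-ratio test will not be used. If the redacted text already contains an adjusted analysis with intervals, confirming this is enough.

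The cost is one additional model specification and its output, with no new data. It is close to the Section 8.7 ANCOVA but not identical: the outcome is binary and the covariate is log-transformed. The SAP should acknowledge that fitted values may fall outside 0-1 and that pooled intervals may be somewhat conservative.
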